3.1.2 Study procedures

Research assistants (RAs) will screen and recruit participants in the waiting area prior to consultation (Day 0). Following children's caregiver informed consent, the RA will record participant name, contact details, sociodemographic details and reason for attendance prior to consultation. In case of critical and emergency cases, children will be seen immediately by the HCP. The clinical consultation will be conducted by HCPs, who in the post-intervention phase will have been advised to use the devices.

After consultation, the RA will extract information from clinical records, the caregiver and/or medical records and will document them in the database. This information includes final diagnosis, oxygen saturation and results of laboratory investigations, prescribed medication, referral or follow-up advice and usage of pulse oximeter and/or CDSA.

Follow-up at Day 7 will be conducted by phone by an RA. If phone follow-up fails, three attempts will be made on the subsequent three days to reach the caregiver. Community mechanisms to facilitate follow-up (such as arranging a call with a community health worker) will be used, with consent, for caregivers without access to a phone. A structured questionnaire will be administered to assess the primary and secondary outcomes, including details of any government or private hospital admission. In case of non-recovery, if the child is still at home, the study team will advise the family to return to the PHC clinic for a follow-up consultation. Refer to "Participant timeline" section of the Protocol for additional details.

3.1.3 Study intervention

- ξ Pulse oximetry embedded into CDSA
 - ο Pulse oximeters, with guidance (integrated into CDSA), training and mentorship
 - ο Tablet-based CDSAs, with guidance, training and mentorship
 - ο Refresher training on latest national / IMCI guidelines integrated with pulse oximetry and CDSA training

3.1.4 Outcomes

This section provides an overview of the outcomes as listed in the protocol.

Primary outcomes

- ξ Proportion of children referred by a primary healthcare provider to a higher level of care at Day 0 consultation
- ξ Proportion of children prescribed an antibiotic at Day 0

Secondary outcomes

- ξ Proportion of children with a severe complication by Day 7
- ξ Proportion of children admitted to hospital within 24 hours of the Day 0 consultation and as a result of a referral (this is a proxy for 'appropriate referral' of children)
- ξ Proportion of children cured at Day 7 follow-up
- ξ Proportion of children who completed referral as reported at Day 7 follow-up

Other outcomes of interest – hypoxaemia (in post-intervention only)

- ξ Proportion of children with severe ($\text{SpO}_2 < 90\%$), moderate ($\text{SpO}_2 90 – 91\%$) and mild ($\text{SpO}_2 92 – 93\%$) hypoxaemia, adjusted for sites at high altitude
- ξ Proportion of children with hypoxaemia (according to differing cut-offs) with severe complication
- ξ Proportion of children with severe hypoxaemia not meeting any other clinical criteria for severe disease
- ξ Proportion of children referred with hypoxaemia who receive oxygen at hospital

Other outcomes of interest – referral and follow-up

- ξ Proportion of children with non-severe disease referred to a higher level of care on Day 0
- ξ Average length of stay (in days) of children admitted to hospital
- ξ Proportion of children attending scheduled follow-up at the same facility by Day 7
- ξ Proportion of children presenting for unscheduled follow-up to any health facility by Day 7

Other outcomes of interest – antimicrobial prescription

- ξ Proportion of children prescribed a diagnosis-appropriate antibiotic
- ξ Proportion of febrile children tested for malaria at Day 0
- ξ Proportion of malaria positive children prescribed an antimalarial
- ξ Proportion of malaria negative children prescribed an antimalarial
- ξ Proportion of untested children prescribed an antimalarial

Other factors for exploratory analyses

- ξ Additional socio-demographic characteristics, urban / rural location, distance from health facility, key household indicators such as maternal age and education
- ξ Main complaint / symptom categories (including cough / difficulty breathing, fever, diarrhoea and other) and time since onset of symptoms
- ξ Alternative hypoxaemia cut-offs
- ξ Health care provider severity classification
- ξ Facility and health system factors – type of facility, health care provider qualification and previous training

These exploratory analyses follow outside the scope of this statistical analysis plan and they will not be detailed further here but in a separate document.

3.2 Randomisation

This is not a randomised study so no randomisation was performed.

3.3 Blinding

This is an open-label study.

3.4 Sample Size

The sample size for the quasi-experimental pre-post study is calculated separately for each country, based on comparison between pre- and post-intervention periods. The following assumptions are used:

- ξ power 80%
- ξ alpha level of 0.05
- ξ pre-intervention referral to a higher level of care 3%, with a minimum detectable difference of 50%
- ξ pre-intervention antibiotic prescription of 60%
- ξ intra-cluster correlation coefficient (ICC) of 0.005 for referral and 0.05 for antimicrobial prescription
- ξ Kenya – estimated average cluster size of 230 children / month (assuming a cluster ratio of health centres : dispensaries 1:2, with 100 / month in dispensaries and 500 / month in health centres)
- ξ Senegal – estimated cluster size of 170 children per month

For the referral primary outcome, we therefore initially estimated requiring the following sample size:

- ξ Kenya – 17 facilities, recruiting an average of 690 children per quarter per facility, equating to 11,730 children per quarter
- ξ Senegal – 18 facilities, recruiting an average of 510 children per quarter per facility, equating to 9,180 children per quarter

For the antibiotic prescription primary outcome, this would enable a minimum detectable reduction of 18% in Kenya and Senegal.

Following lower than anticipated recruitment in the pre-intervention period, sample size calculation was revised. As a result, two additional facilities were added per country and the pre-intervention period was extended from an initially anticipated 3 months to a 6 – 8 month period. A decision was also taken to target a post-intervention sample size of at least the same as the pre-intervention sample size, as well as a minimum duration of 9 months post-intervention to allow for stabilisation over time and some seasonal overlap of pre- and post-intervention periods.

3.5 Framework

The quasi-experimental pre-post study is based on the hypothesis that the intervention will result in a reduction in adverse health outcomes through better treatment and referral

decisions, and an improvement in quality of care through the rational use of essential medicines and improvements in the health worker and caregiver experience.

3.6 Statistical interim Analysis and stopping Guidance

No interim analysis is planned for this study.

3.7 Timing for Analysis

The final analysis will take place once all children have received a minimum of 7 days of follow-up. A pooled cross-country analysis will be conducted as well as individual country analyses.

3.8 Timing for Baseline and Outcome Assessments

Baseline is defined as the date of enrolment (Day 0) and time will be measured from this point.

Follow-up will occur 7 days after Day 0. As defined in the protocol, a window of + 3 days applies to Day 7 follow-up. Refer to “Participants timeline” section of the protocol for more details.

The components (i.e. referral and antibiotic prescription) required for the analysis of the primary outcomes will be assessed at Day 0.

4 STATISTICAL PRINCIPLES

4.1 Confidence Intervals and p-Values

Results estimates of primary and secondary outcomes will be presented along with the associated two-sided 95% confidence intervals.

4.2 Intervention adherence and Protocol Deviations

While in Kenya pulse oximeter was indicated for all children, in Senegal, pulse oximeter was indicated for all young infants and for older children with cough/difficult breathing or red/yellow IMCI classification. Cough/difficulty breathing and red/yellow IMCI classification are defined two ways, based on signs and symptoms as reported by the caregiver pre-consultation or on diagnosis made by the healthcare provider during the consultation. These definitions are detailed in a separate document and both will be used, separately, to assess intervention adherence.

Adherence will be evaluated on the basis of pulse oximeter and CDSA use when indicated.

- ξ Pulse oximetry adherence will be evaluated primarily using information on SpO2 values from clinical records. Pulse oximetry will be considered used if the RA has found any SpO2 recording (value readable or unreadable). Pulse oximetry will be considered not used if the RA did not find any recorded SpO2. Adherence will be additionally evaluated based on pulse oximetry use as reported by the caregivers.

- ξ CDSA adherence will be evaluated by comparing the number of children enrolled and the number of children recorded into the CDSA database. These data will be used to explore further and in more details adherence to the CDSA, but outside the scope of this SAP and it will be detailed in a separate document.

Adherence will be reported overall and weekly by facility.

The following information will be summarised by arm to evaluate deviations to the study protocol:

- ξ Number and percentage of caregivers for which no Day 7 follow-up was attempted.

More general deviations will be recorded by the study team in a study deviation log and categorised into minor and major.

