	Medical history recorded in clinical notes and / or facility registries	TIMCI-05b						
	Chief complaints and medical history recorded in CDSA	TIMCI-05c						

Basic measurements & physical exams	Basic measurements and physical exams recorded in clinical notes and / or facility registries	TIMCI-06a						
	Basic measurements and physical exams recorded in CDSA	TIMCI-06b						
Respiratory rate & pulse oximetry	Respiratory rate and pulse oximetry recorded in clinical notes and/or facility registries ²	TIMCI-07a						
	Respiratory rate and pulse oximetry recorded in CDSA ²	TIMCI-07b						
Laboratory investigations	Respiratory rate and oxygen saturation recorded at arrival by referral facility ²	TIMCI-07c						
	Laboratory investigations recorded in clinical notes and / or facility registries ²	TIMCI-08a						
Diagnosis & care management	Laboratory investigations recorded in CDSA ²	TIMCI-08b						
	Diagnosis and care management in clinical notes and / or facility registries (medical records, discharge summaries)	TIMCI-09a						
	Diagnosis and care management recorded in CDSA	TIMCI-09b						
	Diagnosis and care management recorded by referral facility (medical records, discharge summaries)	TIMCI-09c						
Follow-up at Day 7		TIMCI-10						

¹ Data will be collected retrospectively for visits at facilities offering a higher level of care, including district hospitals, any study facility receiving referrals or admitting patients. ² If appropriate for clinical management.

³ The schedule assumes the intervention includes pulse oximetry plus CDSA.

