7.1.1 Quasi-experimental pre-post study

For each participant enrolled in the quasi-experimental pre-post study, data will be captured during the pre- and post-intervention periods according to the different assessments and Case Report Forms (CRFs) described in the visit schedule displayed in **Tab. 4**. A description of the variables collected in each CRF is available in the appendix.

Health facility visits

Quantitative research assistants will use an EDC mobile application to enter the research data of enrolled participants. The quantitative research assistant will collect from the caregiver screening information, information on care seeking behaviour, transport and costs, and clinical presentation and medical history. A number of in-depth sociodemographic and household variables will also be collected either as surrogate measures of household wealth, or known to be associated with health-seeking behaviour and / or child mortality (including maternal

education). Household wealth indicators were selected from DHS and other surveys in the study countries as those which best estimate wealth index that can be directly collected from the mother / caregiver and with a reasonable time vs. reliability trade-off. Data on laboratory investigations (if performed), final diagnosis, prescribed medication, referral or follow-up advice will be extracted from clinical notes and / or facility registers. Quantitative research assistants will seek clarification from healthcare providers only in cases where these variables are not clear from the records. Personally identifiable information (PII), including participant's name and date of birth, as well as caregiver's phone number and physical address, will be collected for linking data and detecting possible duplicates and carrying out the study follow-up.

During the post-intervention period, the research data of participants enrolled in the study will be linked with their CDSA consultation data. Additional information on oxygen saturation will be collected as recorded in clinical notes and / or facility registers. Pulse oximeter device savings will be cross-checked by quantitative research assistants at the end of the consultation where possible.

Follow-up

Quantitative research assistants will conduct the phone follow-up interviews using an EDC mobile application. Personally identifiable information (PII) will be used for contacting caregivers. A window of +3 days (Day 7 to Day 10) applies to Day 7.

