7.1.2 Routine data

CDSA individual consultation data

Routine individual consultation data will be recorded in the CDSA in all intervention facilities in the post-intervention period. As part of the intervention, healthcare providers will be asked to use MedAL-R during their consultations. When they do so, they will routinely enter all data necessary for the clinical management of children 0 – 59 months of age into MedAL-R. Data used within TIMCI will cover clinical presentation (including symptoms and dangers signs), medical history (including HIV and TB status if known), all physical exams and measurements relevant for clinical assessment (including pulse oximetry), and laboratory investigations. Automated recommendations from CDSA on diagnosis and child management will also be collected, as well as healthcare provider's agreement or disagreement with these recommendations and possible additional diagnoses and treatments, which will be manually entered. A description of the variables extracted from CDSA is available in the appendix.

HMIS aggregate facility data

HMIS data will include the total number of outpatient consultations – for all patients and for children 0 – 59 months of age (disaggregated by new and follow-up visit if possible) –, disease burden, and any other relevant indicators if available (such as referral rate or mortality rate), disaggregated by age and sex if routinely collected with this granularity.

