6.4 Additional analyses

Primary outcomes will be further presented by adherence and indication groups (e.g. children for which pulse oximetry was indicated and was used, children for which pulse oximetry was indicated but was not used, etc.).

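### The SAP's rule for pulse oximetry use leaves out SpO2 entered in the CDSA, so readings held only in the tablet may be counted as non-use

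*SAP*

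**What the plan says.** SAP 4.2 names one primary source for oximetry adherence: "Pulse oximetry adherence will be evaluated primarily using information on SpO2 values from clinical records". Any SpO2 recording, legible or not, counts as use. The converse is stated just as plainly: "Pulse oximetry will be considered not used if the RA did not find any recorded SpO2". A second measure follows: "Adherence will be additionally evaluated based on pulse oximetry use as reported by the caregivers".

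The CDSA database appears in the same section, but for a different purpose: "CDSA adherence will be evaluated by comparing the number of children enrolled and the number of children recorded into the CDSA database". More detailed work on adherence to the CDSA is left to a separate document. Adherence is to be reported in total and week by week for each facility.

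The protocol describes a second place where SpO2 is held:

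- On consultations in intervention facilities, section 7.1.2 says of providers that "they will routinely enter all data necessary for the clinical management of children 0 – 59 months of age into MedAL-R", and it names pulse oximetry among the measurements.
- Tab. 4 in section 6.5.1 has a form, TIMCI-07b, for "Respiratory rate and pulse oximetry recorded in CDSA". It is separate from TIMCI-07a, which covers notes and registries.
- For the post-intervention period, section 7.1.1 says that "the research data of participants enrolled in the study will be linked with their CDSA consultation data".

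The classification from SAP 4.2 is used again in three places. Section 4.3 reports safety by use of the intervention, and section 6.5 refers back to 4.3 for the harms tables. Section 6.4 presents the primary outcomes by adherence and indication, with one group being "children for which pulse oximetry was indicated but was not used".

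**The concern.** Oximetry is delivered as part of the CDSA, so the tablet is a natural place for the reading to be written down. If a provider enters it there and does not copy it to the card, notes or register, the primary rule may record that oximetry was not used. The adherence figure would then partly measure copying habits rather than delivery of the intervention.

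Two inconsistencies could follow. First, a child could count as adherent for the CDSA and non-adherent for oximetry while an SpO2 value sits in the same CDSA record. Second, protocol section 7.3.2 plans to describe oximetry use in facilities outside the pre-post study from routine CDSA data. Use would then be measured from the tablet in those facilities and from clinical records in the study facilities, and the two figures would not be comparable.

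At stake are the adherence report, including its comparison of facilities, and the meaning of the non-use group in the tables of SAP 4.3, 6.4 and 6.5.

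**Working it through.** **Sources side by side**

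| Possible source of SpO2 for an enrolled child | Where described | Named in SAP 4.2 for oximetry use? |
|---|---|---|
| Clinical notes or facility registers (TIMCI-07a) | Protocol 6.5.1 Tab. 4; 7.1.1 | Yes, as clinical records (primary) |
| Caregiver report of use | SAP 4.2 | Yes (additional) |
| CDSA consultation (TIMCI-07b), linked to the child | Protocol 6.5.1 Tab. 4; 7.1.1; 7.1.2 | No; CDSA database used only to count children for CDSA adherence |
| Readings stored on the oximeter, cross-checked where possible | Protocol 7.1.1 | No |

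The SAP therefore omits by name a source that the protocol treats as distinct and plans to link.

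**Illustration of size**

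The documents give no adherence rate and no tablet-only share, so there is no stated figure to reproduce. Both inputs below are assumptions.

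- U = true oximetry use among children for whom it was indicated.
- t = share of those readings held only in the tablet.
- Reported use = U × (1 − t).
- Share of the non-use group that was in fact measured = U × t / (U × t + 1 − U).

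With U = 80%:

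| t | Reported use | Non-use group in fact measured |
|---|---|---|
| 0% | 0.80 × 1.00 = 80% | 0% |
| 5% | 0.80 × 0.95 = 76% | 0.04 / 0.24 = 17% |
| 10% | 0.80 × 0.90 = 72% | 0.08 / 0.28 = 29% |
| 25% | 0.80 × 0.75 = 60% | 0.20 / 0.40 = 50% |

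The result also depends on U. At t = 10%:

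- U = 60%: reported use is 0.60 × 0.90 = 54%, and 0.06 / 0.46 = 13% of the non-use group was measured.
- U = 90%: reported use is 0.90 × 0.90 = 81%, and 0.09 / 0.19 = 47% of the non-use group was measured.

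Two things follow for any inputs. Since 1 − t cannot exceed 1, missed tablet readings can only lower the records-based figure. For a given t above zero, the non-use group is more contaminated the higher true use is, because few children are then truly unmeasured.

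**Where the classification does not reach**

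SAP 4.3 applies the intention-to-treat principle to all analyses, and the models in SAP 6.2.1 compare periods, not users with non-users. No primary or secondary effect estimate takes the oximetry classification as an input.

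**The case against.** The strongest reply is that misclassification is inferred rather than shown. SAP 4.2 does not define clinical records, and a broad reading could include the tablet. The staff symbols in Tab. 4 are missing from the text examined here, so one cannot tell who completes TIMCI-07b; if the research assistant does, a CDSA value could be one that the assistant found. Protocol 7.1.1 also has assistants cross-check oximeter readings where possible, and SAP 4.2 does not say whether such a reading counts as a recording. Caregiver report does not depend on copying from the tablet, so disagreement between the two measures would hint at under-recording. If providers routinely write SpO2 in the register, the effect is close to zero.

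Much of this stands. It means that the rule may misclassify children, not that it does. It does not remove the point: Tab. 4 keeps notes and registries apart from the CDSA, and a reader cannot tell from SAP 4.2 which sources count. Caregiver report is a separate evaluation and does not correct the primary classification. The detailed CDSA work that is deferred concerns adherence to the CDSA, not oximetry use.

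Keeping oximetry adherence separate from CDSA adherence is also defensible, which is a reason to retain the records-only figure rather than discard it.

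A reader might infer that the primary result is compromised. The documents do not support that. The outputs affected are descriptive, and the used and not-used groups reflect providers' choices, so even a perfect split would not carry a causal reading.

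**Conclusion.** The point holds as a gap in the definition. As written, SAP 4.2 does not name linked CDSA SpO2 as evidence of oximetry use, and a tablet-only reading may be counted as non-use unless clinical records is meant to include the tablet. Any such misses push reported adherence down, never up, and may mix measured children into the non-use group of the tables in SAP 4.3, 6.4 and 6.5.

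The size cannot be stated. It runs from near zero upward with the tablet-only share, and the figures in the working rest on assumed values for both true use and that share. A reader might conclude that adherence will certainly be understated, or understated most where facilities rely on the tablet. The documents give no data on recording habits, so neither can be claimed. The change is worth making because it is specific and uses a linkage the protocol already plans, not because a large bias has been demonstrated.

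**What to change.** Replace the rule in SAP 4.2 with wording such as:

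> Oximetry counts as used if the research assistant finds an SpO2 recording (readable or unreadable) in the clinical record, or if the child's linked CDSA consultation contains one. It counts as not used only if neither source does.

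Apply this classification in SAP 4.3, 6.4 and 6.5. Beside it, report the records-only figure and the proportion of enrolled children linked to a CDSA consultation, overall and by facility. State what clinical records covers. If the tablet was always meant to be included, that statement still belongs in the SAP so that the analysis can be reproduced.

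The cost is a change of wording and a data merge. No new data collection is needed. The merge should not be assumed trivial: the protocol plans the linkage but does not show that it is complete. Under the either-source rule, capture will vary with linkage completeness across facilities, and this could itself affect comparisons between them. Reporting the linked share by facility discloses that problem but does not remove it, which is why the records-only figure should stay alongside.
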